In this regard, evidence-based approaches, such as strengths-based care management, could be added to BIs to enhance efficacy; however, to be feasible in the ED and VHA, service delivery needs to be modified to minimize demands on VHA providers. Peers are ideal candidates for providing alcohol BIs and post-ED strengths-based assistance in the form of peer mentoring because of their shared experiences with patients. Peers can serve as role models and provide emotional support resulting in greater self-efficacy, healthy behavior change, and linkage to needed services.^{9,10} *Therefore, the objective of this proposed study is to conduct a hybrid randomized controlled trial (RCT) to determine the efficacy of an peer-delivered alcohol intervention starting in the ED with peer-delivered brief alcohol advice, combined with a continuing 6-session program of post-ED strengths-based peer mentorship, compared to standardized brief advice in the ED only, to facilitate reduction in risky drinking and linkage and engagement in primary and/or specialty alcohol treatment services care, if needed – an **Alcohol Peer-Mentor Intervention (APM; n=225)**, compared to **Brief Advice in the ED only (BA; n=225)** condition. The primary specific aims are to:*

Aim 1: Determine the efficacy of the ED APM intervention compared to BA on subsequent TLFB drinking frequency reports, including number of drinking days per month, number of drinks per drinking day, and number of binge drinking days at 3-, 6-, and 12-months post-baseline. **Hypothesis:** Veterans with hazardous drinking who are randomly assigned to APM will have significantly greater reductions in alcohol use as measured by TLFB reports, compared to those assigned to BA at 3-, 6-, and 12-month follow-ups.

Aim 2: Determine the impact of the APM intervention on linkage to primary and specialty alcohol treatment services care, mental health symptoms and functioning at 3-, 6-, and 12-months post-baseline. **Hypothesis:** Veterans with hazardous drinking who are randomly assigned to APM will be significantly more likely to link and engage in primary, specialty care, and other VHA supportive services and to have improvements in mental health symptoms and functioning.

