Description of Study Site. The proposed study will recruit from the ED in the VA Ann Arbor Healthcare System (VAAAHS). The following numbers are based on data from 2015. This ED treated a total of 10,653 patients drawn from a relatively wide geographic area that included western Wayne County (Detroit area), as well as several mid-sized cities and rural communities. Patients seen had the following characteristics: 9% female; 75% White, 10% African American, and 3% of another race (mainly multiple races); about 2% Hispanic. The VAAAHS ED is very supportive of this research project. Only one site will be included in this study to enhance our ability to ensure fidelity of peer-delivered intervention content through closer supervision and monitoring. If shown to be efficacious, we will scale up in order to add many sites later through an implementation study.

Inclusion Criteria for Screening. (1) adults age 18 years of age or older presenting for care in the Ann Arbor VHA ED; and (2) medically stable and able to provide informed consent per Mini-Cog assessment score of 3 or more.

Inclusion Criteria for the RCT. *Individuals will be eligible to participate in the RCT if they: (1) have an AUDIT-C score of 4 or more for men and 3 or more for women in the prior 3 months, indicating that they meet criteria for hazardous use⁵⁵; and 2) have a telephone and/or the ability to provide information about individuals who can help contact the participant. Homeless Veterans may not have a telephone but will be asked for individuals who can help to contact them (e.g. shelter, family, friends, etc.). Importantly, the study will include not only those with less severe hazardous drinking but also those with more harmful use and severe problems to address the problems and needs of Veterans who can most benefit from linkage to primary and secondary care. Furthermore, a recent study validates the full AUDIT among Veterans, with scores of 14 and 10 (male, female, respectively) indicating an AUD.⁵⁶ However, to be inclusive and sure that all Veterans who may need specialty care have the information to get to that care, we will set scores for specifically recommending specialty care to the Veteran participant more conservatively at 10 for men and 8 for women.* Both study conditions will receive information on accessing VHA primary/specialty services.

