Exclusion Criteria for Screening. (1) patients who do not understand English; (2) prisoners; (3) patients currently in or having received substance abuse treatment in the past 3-months per medical record; (4) patients currently in or having received peer services in the past 3-months per medical record; (5) pregnant women; (6) patients deemed unable to provide informed consent as stated above; and (7) profound psychotic symptoms and/or cognitive deficits that would prevent patients from understanding the content of the intervention and/or assessments.

Exclusion Criteria for RCT. (1) individuals currently active in or having received alcohol or other substance abuse treatment in the past 3-months per self-report in screening; (2) patients currently in or having received peer services in the past 3-months per self-report screening.

Participants may be excluded at the discretion of the Principal Investigator based on participant or study staff best interest (e.g., if participant should become physically or verbally aggressive towards study staff, or if the study staff know a patient or their family personally, in order to fully ensure participant privacy).

Participant Remuneration. Participants will be remunerated \$5 for completion of the screening instrument and \$25 for completion of the baseline assessment. Participants will be provided \$10 remuneration for completing the baseline assessment in-person the same day of enrollment in the ED. Remuneration will also include: \$25 for each of the 3-month and 6-month surveys, \$10 for each of the 3-month, 6-month, 12-month TLFB interviews, \$40 for the 12-month survey for a total of \$160.

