Week	Session Focus
1: Triggers and Motives	
 Solicit Veteran's issues and questions prompted by initial meeting in the ED Begin the process of identifying Veteran's strengths, abilities, skills Address Veteran's personal needs and barriers to health care Identify triggers and motives for alcohol use (e.g., feelings, people, places, activities) Identify initial coping strategies Encourage linkage to primary and/or specialty care as needed Summarize the major points in session Set up next weekly meeting with flexibility to meet more often for specific help
2: Coping and Quality of Life	
 Solicit Veteran's issues & questions since last contact Continue to emphasize Veteran's strengths Encourage cutting down alcohol use and/or assessment and treatment linkage Review triggers and motives for alcohol use (e.g., feelings, people, places, activities) Further explore coping strategies to increase quality of life and reaching goals Encourage contact with primary and/or specialty care Summarize the major points of the session Set up next weekly meeting with flexibility to meet more often for specific help
3: Problem Solving & Overco ming Barriers	
 Solicit Veteran's issues and questions since last contact Identify and address Veteran's personal needs and relationship to drinking Review service options and barriers to seeking health care Problem solve solutions to barriers and encourage service use Summarize the major points of the session Set up next weekly meeting with flexibility to meet more often for specific help
4: Social Support	
 Solicit Veteran's issues and questions since last contact Encourage decreased alcohol use with strategies and linkage to care Identify existing sources of social support Explore options for obtaining additional support Encourage contact with primary and/or specialty care Set up next weekly meeting with flexibility to meet more often for specific help
5: Leisure Activiti es and Work	
 Solicit Veteran's issues and questions since last contact Encourage decreased alcohol use with strategies and linkage to care Identify enjoyable, alternative activities to drinking alcohol Examine work concerns and work/life balance Encourage contact with primary and/or specialty care Set up next weekly meeting with flexibility to meet more often for specific help

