6: Plannin g for the Future	
 Solicit Veteran's issues and questions since last contact Encourage decreased alcohol use with strategies Review coping, social support and leisure options Review solutions to barriers and service options Encourage contact with primary and/or specialty care Summarize progress and plans

current usual practices of ED-based brief interventions and current staffing models. One-session brief clinician advice by a social worker in the ED has had mixed and modest positive effects, but it remains the cornerstone of most alcohol brief interventions in large health systems. Thus, the comparator will be real-world relevant, potentially helpful yet also conservative in terms of the extent to which it can influence longer-term drinking outcomes.

Peer Mentor Hiring, Training, and Supervision. Peer mentors will be hired according to current policy guidelines provided by the VHA Office of Peer Support Services. As is standard practice in VHA programs, we will not require the peer specialist to be matched with study patients on specific demographic characteristics (e.g. military service era, gender) because these requirements introduce practical and ethical hiring challenges and are unlikely to be upheld if the program is implemented across VA facilities with existing peer specialists. However, preference will be given to peer specialist applicants with experience with hazardous drinking/substance use disorders.⁵⁷ Peer specialists will complete standardized VA peer support training and certification through a training program approved by the Office of Peer Support Services. An example training

Peer Mentor Content. Peer mentors will deliver the brief advice in the ED and will initiate conversations with the patient for up to 6-sessions over 2 months post-ED visit. Strengths-based discussions will include a combination of scripted and open-ended content to best facilitate reductions in drinking and engagement across severity (see Table 1). All sessions will be audiotaped and will emphasize strengths and goals, focusing on reducing/stopping alcohol use and linkage to care and barriers (e.g., transportation, going with the Veteran to the first appointment, housing, job or family issues, etc.).

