Data Management. The project's data manager will conduct all data management and analysis activities under the supervision of Drs. [name] and [name]. Research staff will use double entry procedures and reconcile discrepancies. Data cleaning will be conducted throughout data collection to ensure a quality final dataset for analysis. Statistical Analysis System (SAS) will be used to examine and prepare data for the analysis.

General analytic approach. Hypotheses will be planned a priori, and will be limited to the examination of a limited number of outcomes. We will utilize an "intent-to-treat" approach. All analyses will use two-sided tests because it is possible that the APM participants might have worse outcomes compared to CBA participants. Analyses will begin with descriptive data analyses to determine distributions of key variables, to collapse categories, if necessary, and to review data for outliers and clear anomalies. Tests for linearity, independence, missingness, and distributional assumptions will also be performed. Normalizing transformations of the dependent variables will be utilized, if necessary. We will validate the randomization scheme by comparing the initial groups on key variables that could be associated with the outcomes. Where we identify significant differences between groups, we will adjust for these variables, as well as other addictions treatment received if it was not initiated by referral from the APM or CBA clinician (and thus a potential mediator of effect). Prior to fitting any analytic models, a graphical exploration of the outcome variables will be conducted to select the appropriate models based on variable distributions.

Missing data. Every effort will be made to minimize missing data. Where we have missing covariates that are necessary for analysis, we will perform multiple imputation of missing data and combine the results from 5 imputations based on Rubin's method to produce an estimate and the corresponding confidence interval accounting for missing data uncertainty.⁸⁸ For follow-up attrition, the proposed mixed-effects regression model will allow the use of data from all participants (not just those with complete follow-up) and provide unbiased

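### Adjusting for addictions treatment received during the trial can stop the group coefficient from being the total effect of assignment, and the Aim 1 model does not list that covariate

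*Combined protocol and SAP*

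**What the plan says.** **Data analyses, General analytic approach.** The plan adopts intent-to-treat. It then says "We will validate the randomization scheme by comparing the initial groups on key variables that could be associated with the outcomes", and continues: "Where we identify significant differences between groups, we will adjust for these variables, as well as other addictions treatment received". The qualification on the treatment covariate is "if it was not initiated by referral from the APM or CBA clinician (and thus a potential mediator of effect".

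**Data Analysis for Aim 1.** The independent variables named are the baseline value of the outcome, time since randomisation and group, with a random effect for the peer or clinician. The group coefficient is said to estimate the effect averaged over follow-up. Addictions treatment is not named. Data Analysis for Aim 2 takes over the same independent variables.

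**How the arms differ.** The Aim 2 hypothesis is that Veterans assigned to APM "will be significantly more likely to link and engage in primary, specialty care, and other VHA supportive services". Session 1 of Table 1 includes "Encourage linkage to primary and/or specialty care as needed", and each of the other five sessions also has an item promoting care or service use. Peer Mentor Content adds help with barriers, such as "going with the Veteran to the first appointment". The Brief Advice Condition has no sessions after the ED visit. On service information the arms are alike: "Both study conditions will receive information on accessing VHA primary/specialty services".

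**Entry.** Exclusion Criteria for RCT removes "individuals currently active in or having received alcohol or other substance abuse treatment in the past 3-months per self-report in screening".

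**The concern.** The treatment covariate is most naturally post-randomisation. A trial referral cannot come before enrolment, so the exemption has a purpose only for treatment received afterwards, and current or recent treatment is an exclusion. Treatment more than three months before entry remains possible, and the record review covers one year before entry, but the exemption would do nothing for it.

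The authors saw the mediator problem but exempted only one route, treatment begun by referral. A participant whom a peer encourages, and who then seeks care without a referral, falls outside the exemption, although the assignment produced that treatment. The referred label may also depend on arm, because APM has up to six more contacts in which a referral could be made. That is an inference. It is also unclear whose referrals count in the comparison arm: the exemption speaks of a clinician, the Brief Advice Condition has a research assistant give the advice, and the Human Subjects section says an ED clinician or the peer mentor.

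The sentence can be read as always adjusting for treatment, or as adjusting only where the groups differ significantly. The second reading gives no protection, because a difference between arms in treatment is what mediation would produce.

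At stake are the meaning of the primary coefficient and a covariate choice left open until after the data are seen.

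**Working it through.** **1. The plan's own figure.** Power and Sample Size Calculations gives 450 randomised, 80% retained (360, so 180 per arm), two-sided alpha 0.05 and 80% power at d = 0.30. Normal approximation: Φ(0.30 × √(180/2) - 1.96) = Φ(0.886) = 0.812. The t-test gives 0.810. The figure reproduces, and nothing here changes it.

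**2. What adjustment does.** If nothing else links treatment to the outcome,

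adjusted coefficient = total effect - b × (pA - pB),

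where b is the effect of non-referred treatment on the outcome and pA and pB are its rates in APM and BA. The documents give none of these, so the values below are assumptions:
- Equal rates: -0.30 - b × 0 = -0.30, so no bias.
- 20% v 10%, b = -0.3: -0.30 + 0.3 × 0.10 = -0.27 (power about 0.73).
- 30% v 10%, b = -0.6: -0.30 + 0.6 × 0.20 = -0.18 (power about 0.40).

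**3. Simulation with treatment related to motivation.** A linear model of outcome on arm was fitted with and without non-referred treatment, with 180 per arm and 4,000 trials per scenario. Assumed: treatment effect -0.3 SD unless stated; correlation 0.5 between motivation and seeking; motivation effect -0.3 SD per SD; the referred label random among seekers within arm. The non-referred rate is seeking × (1 - share labelled referred). For example, 20% × (1 - 0.70) = 6% in APM and 20% × (1 - 0.20) = 16% in BA.

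| Scenario (APM v BA) | Non-referred treatment | Adjusted estimate | Rejection rate (unadjusted) |
|---|---|---|---|
| Null; equal seeking and labelling | equal | -0.001 | 5.0% |
| Null; 20% seek; label 60% v 40% | 8% v 12% | -0.021 | 5.1% |
| Null; 20% seek; label 70% v 20% | 6% v 16% | -0.053 | 8.2% |
| Null; 20% seek; label 70% v 0% | 6% v 20% | -0.077 | 10.3% |
| Null; 10% seek; label 70% v 20% | 3% v 8% | -0.028 | 6.1% |
| True -0.30; seek 30% v 20%; label 20% both | 24% v 16% | -0.254 | 66.7% (78.1%) |
| True -0.30; seek 35% v 20%; label 20% both; treatment effect -0.4 | 28% v 16% | -0.227 | 56.0% (78.9%) |
| True -0.30; seek 30% v 20%; label 30% v 20% | 21% v 16% | -0.275 | not shown |
| True -0.30; seek 30% v 20%; label 40% v 20% | 18% v 16% | -0.289 | not shown |
| True -0.30; seek 30% v 20%; label 50% v 20% | 15% v 16% | -0.304 | 81.2% (78.8%) |
| True -0.30; seek 30% v 20%; label 70% v 20% | 9% v 16% | -0.336 | 87.9% (79.6%) |

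The bias follows the difference in non-referred treatment: more of it in APM shrinks the estimate, less of it inflates the estimate. If heavier drinkers, rather than motivated ones, seek care, the null estimates lie between -0.01 and +0.02 SD with rejection rates of about 5%.

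**4. The other reading of the sentence.** If adjustment happens only when non-referred treatment differs at p < 0.05:
- Seeking 30% v 20%: triggered in 48.2% of trials, mean estimate -0.267, power 70.2%.
- Seeking 35% v 20%: triggered in 79.0%, -0.235, 58.3%.
- Null, label 70% v 20%: triggered in 87.4%, -0.050, type I error 7.8%.

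**5. Closer to the Aim 1 model.** Using the mean change score over three follow-ups with the baseline covariate (assumed baseline correlation 0.5, within-person correlation 0.6, no provider effect), the bias agreed within 0.01 SD: -0.053, -0.259 and -0.305 for the null 70% v 20% case, the 30% v 20% seeking case and the 50% v 20% label case. Aim 2 visit counts were not simulated.

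**The case against.** The strongest reply is that the section specific to Aim 1 governs, and it does not contain the covariate. If so, the primary result is unaffected and the sentence only needs tidying. But that section says what the variables will include, which need not be exhaustive, and General analytic approach is written for all analyses. Neither text yields to the other.

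Second, the exemption covers the route for which the team has evidence. Preliminary Studies reports that warm referral to case management raised assessment (OR 1.79) and engagement (OR 1.48). If all extra APM treatment comes by referral, non-referred treatment is balanced. With 27% v 20% treated (OR 1.48 on an assumed 20%) and every extra APM episode labelled referred, the adjusted and unadjusted estimates are both -0.304, and the null rejection rate is 5.3%. This stands as a no-bias case. It requires that peer encouragement always counts as referral, which the plan does not define.

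Third, those odds ratios could anchor milder scenarios. OR 1.48 with 20% labelled referred in both arms gives -0.27 (power 72%) on a 20% base and -0.28 (75%) on a 10% base. They come from another population and are not uptake rates for this trial. For comparison, 30% v 20% is an odds ratio of (0.30/0.70)/(0.20/0.80) = 1.71, between the two reported values.

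Fourth, the larger type I errors need very unequal labelling with equal seeking. That is so: 70% v 0% is an extreme, and 60% v 40% does no visible harm.

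**Conclusion.** The point holds and should be fixed. Participants are still analysed as randomised. But a stated rule would put a post-randomisation variable that assignment may affect into the model, and the coefficient would then no longer be reliably the effect that the Aim 1 section says it estimates. The case rests on the text: the exemption covers referral only, APM promotes care-seeking by other means, and the two analysis sections are not reconciled.

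Neither sign nor size can be fixed from the documents. Under the assumptions above, the bias is zero when non-referred treatment is balanced, about 0.05 to 0.07 SD towards the null when APM raises self-initiated treatment, and 0.02 to 0.08 SD in APM's favour when only the labelling differs and motivated patients seek care. The two can offset each other. Confidence is medium, because the timing of the covariate and the trigger for adjustment have to be read from an ambiguous sentence.

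**What to change.** - In General analytic approach, delete the phrase that adds other addictions treatment, together with its referral exemption.
- Add one sentence: apart from group, time and the planned random effect, the primary Aim 1 and Aim 2 models use only covariates measured before randomisation, and the group coefficient estimates the total effect of assignment. This limits model covariates. It does not restrict the pattern-mixture or imputation methods under Missing data.
- Report addictions treatment outside the study by arm, from the Treatment Services Review and the record review already planned.
- Present any treatment-adjusted model as a labelled mediation or sensitivity analysis. Split it by referral only if existing records identify who initiated treatment in the same way in both arms.

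**Cost.** One phrase is deleted and one sentence added, with no new participants or data. No listed measure is said to record who initiated treatment. Progress notes, session recordings or the record review might; if they do not, the referral split is left out. The stated power basis is unchanged (0.81 at d = 0.30 with 180 per arm).

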ED Staffing / Subject Accrual. Because it is not possible to staff the project continuously (168 hours/week), this study will use the following sampling frame that has been used successfully in our previous ED research to ensure obtaining a representative sample of Veterans presenting to the AAVA ED. Project staff in the ED will recruit patients for the study 5 days per week between the hours of 10AM to 6PM. The majority of the recruitment time will be spent in the ED between 10AM and 6PM because 65-70% of patients enter the ED during those hours. In addition, another three days/week will include a weighted sampling of recruiting between either 7AM-3PM or 3PM-11PM time period. Thus, a total of 8 shifts (8 hours each) will be staffed each week to recruit, consent, screen patients, conduct baseline assessments, and deliver brief advice. Based on our previous ED studies where we have used similar staffing schedules we expect to accrue the following numbers: 30 months of screening x ~130 patients/month approached = 3,900; it is expected that 80% (n=3,120) will agree to participate and will be screened. We conservatively expect that 15% of the screened patients will have a positive screen and will be randomized (450 randomized; 225 per group). Randomization Procedures. Stratified random assignment to conditions will be by sex and presence of an AUD (yes/no) defined as a score of 14 for men and 10 for women on the AUDIT. Randomization by sex will be used because men and women generally differ in their rates and nature of alcohol use, problems, and outcomes. Random assignment will also be stratified based on meeting criteria for past year AUD (yes/no) because of potential differences in problem severity and potential intervention response. Randomization will proceed in blocks of 10 within study cells, in order to equalize randomization over time. Follow-up staff will be blind to condition. Participants in both conditions will receive written information regarding alcohol and VHA resources and be re-contacted to complete 3-, 6-, and 12-months follow-ups.

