parameter estimates that account for missing data under the missing-at-random assumption.⁸⁹ We will look for non-random attrition, and if we find, for example, attrition rates to depend on a baseline covariate, we will include this covariate in the model. If we find attrition to depend on treatment use or ideation at prior assessments, we will utilize an appropriate pattern mixture model or multiply impute data based on an appropriate pattern mixture model assumptions based on the observed missing data pattern.⁸⁸

Aim 1: Determine the efficacy of the ED APM intervention compared to BA on TLFB drinking frequency reports at 3-, 6-, and 12-months post-baseline. **Hypothesis:** Veterans with hazardous drinking who are randomly assigned to APM will have significantly greater reductions in total TLFB drinking frequency reports, compared to those assigned to CBA.

Data Analysis for Aim 1: The primary purpose of Aim 1 is to examine the impact of the intervention on frequency of drinking per TLFB interview. This outcome will likely follow the assumptions required for linear regression model, but we will adjust the model type as needed. Assuming this is the case; we will use a linear mixed-effects model and estimate the treatment effect as the difference in the time-averaged TLFB frequencies over the year of follow-up. Because reduction in problem alcohol use is of primary interest, the analysis will model change-scores from baseline in the response variable as dependent variable, and the independent variables will include the baseline values of the response variable, time in months since randomization, and the treatment group indicator. The parameter estimate of the treatment group indicator will estimate the time-averaged treatment effect. *In a second model, we will include an interaction of time by treatment group indicator to formally test the possibility that the effect varies over time. Models will include a random effect for which specific peer/clinician a participant was assigned.*

Aim 2: Determine the impact of the APM intervention on linkage to primary and specialty alcohol treatment services care, mental health symptoms and functioning at 3-, 6-, and 12-months post-baseline, compared to BA. **Hypothesis:** Veterans with hazardous drinking who are randomly assigned to APM will be significantly more likely to engage in primary, specialty care, and other VHA supportive services and to have improvements in mental health symptoms and functioning.

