Data Analysis for Aim 2: The focus of Aim 2 is to study intervention effects on secondary outcome of frequency of primary care and mental health specialty care visits (as two separate outcomes) from the TSR, calculated as an average number of visits per month during each follow-up period. Similar to Aim 1, analyses will generally use a mixed effect model framework. As described above, initial analyses will examine the distribution of outcome measures over follow-up in order to select an appropriate model (e.g. Poisson regression or a related method for counts of visits). Our analysis strategy will parallel Aim 1 in terms of the independent variables, *random effect for peer/brief advice, focus on time-average treatment effects, and additional modeling of interactions of group and time.*

Secondary Aim will determine the mediators (e.g., motivation to change, self-efficacy, coping, social support) of the effect of the intervention and linkage on subsequent alcohol use and alcohol-related consequences. **Hypothesis:** The effect of randomization to APM compared to BA on the primary outcomes (i.e., alcohol consumption and consequences) will be mediated by differences between groups in motivation to change, self-efficacy, and perceived helpfulness of peer support.

Data Analysis for Secondary Aim: *In order to establish temporal ordering, we will examine whether level of the hypothesized mediators at 3 and 6 months post-baseline mediates the effect of random assignment on 6- and 12-month measures of the three primary outcomes of alcohol use behaviors.^{90,91} We will first determine the whether study condition is associated with the hypothesized mediators over the first six months of follow-up and check for a direct effect of the mediators at 3 and 6 months on alcohol use as measured at 6- and 12-months follow-up. We will estimate the indirect effect of the intervention on alcohol use through the mediators and conduct significance testing of this effect using macros created by Preacher and Hayes.⁹²*

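### Beyond the fixed model terms, baseline covariates are chosen by significance tests between arms, which leaves out most prognostic variables and in effect always leaves out the stratification factors

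*Combined protocol and SAP*

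**What the plan says.** All references are to the combined protocol and SAP.

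- **Data analyses, General analytic approach.** "We will validate the randomization scheme by comparing the initial groups on key variables that could be associated with the outcomes". Then: "Where we identify significant differences between groups, we will adjust for these variables". The variables are not listed, and neither the test nor its significance level is given. The same sentence goes on to adjust for other addictions treatment received after randomisation; that is a different matter and is not part of this point.
- **Data Analysis for Aim 1.** The outcome is change from baseline, and "the independent variables will include the baseline values of the response variable, time in months since randomization, and the treatment group indicator". Also: "Models will include a random effect for which specific peer/clinician a participant was assigned".
- **Data Analysis for Aim 2.** "Our analysis strategy will parallel Aim 1 in terms of the independent variables".
- **Missing data.** A second data-dependent route into the model exists: if the team finds "attrition rates to depend on a baseline covariate, we will include this covariate in the model".
- **Randomization Procedures.** "Stratified random assignment to conditions will be by sex and presence of an AUD (yes/no"), in blocks of 10 within cells. The stated reason is that sex and AUD may bear on alcohol outcomes or on response to the intervention. Neither factor is named in the Aim 1 or Aim 2 model.

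**The concern.** A covariate improves the precision of a treatment comparison because it predicts the outcome. Whether it happens to differ between arms in this sample is close to irrelevant to that purpose. If allocation was carried out correctly, every baseline difference is due to chance, so a test at 5% picks each unstratified candidate about one time in twenty, however strongly it predicts drinking. A strong predictor with a baseline p-value of 0.10 stays out; a weak one with 0.04 goes in.

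Two things are at stake. The first is precision that the trial could have from data it already collects. The second is prespecification: with candidates, test and threshold all unstated, the final covariate set is settled only after baseline data by arm have been examined. That fits poorly with the plan's own commitment to a priori hypotheses.

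The stratification factors are a special case. Stratifying forces them to balance, so a rule that looks for imbalance will not find them. Yet they are the variables the design singled out as important, and leaving a prognostic stratification factor out of the model makes the standard error larger than it need be.

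**Working it through.** **Inputs from the documents.** 450 randomised 1:1; 80% retained, so 360 analysed (180 per arm); two-sided alpha 0.05; d = 0.30; stated power 80% (Power and Sample Size Calculations). Blocks of 10 within sex-by-AUD cells (Randomization Procedures). 7.5% female (Human Subjects).

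**Assumptions.** Baseline tests at the 5% level; 5 to 20 independent candidates; added covariates explain a share R² of the variance left after the fixed terms, from 0.02 to 0.30; AUD share 30% or 50%; d expressed on the SD that remains after the fixed terms.

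**1. The plan's own figure.** The noncentrality is d × √(n/2) = 0.30 × √90 = 2.846. The t distribution with 358 df gives 81.0% power (normal approximation 81.2%), and the effect detectable at 80% power is 0.296. The stated 80% for d = 0.30 is reproduced. The power section attaches this figure to total AUDIT score and not to TLFB; that is a separate matter and does not affect the arithmetic.

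**2. Chance of selection.** For one unstratified candidate it is 5% (simulated 4.9–5.3%), so it is omitted about 95% of the time. For at least one of k independent candidates it is 1 − 0.95^k:

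| k | 5 | 10 | 15 | 20 |
|---|---|---|---|---|
| P(at least one enters) | 23% | 40% | 54% | 64% |

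**3. Stratification factors.** Women: 0.075 × 450 ≈ 34, in two cells. Blocks of 10 allow a difference of at most 5 per cell, so at most 22 against 12 of 225 per arm, chi-square p = 0.07. AUD at a 50% share: at most 117 against 107, p = 0.35. In 20,000 simulated trials at each AUD share, neither factor was ever selected.

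**4. Power with a prespecified list.** The noncentrality becomes 0.30/√(1 − R²) × √90:

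| R² of added covariates | 0 | 0.02 | 0.05 | 0.10 | 0.20 | 0.30 |
|---|---|---|---|---|---|---|
| Noncentrality | 2.846 | 2.875 | 2.920 | 3.000 | 3.182 | 3.402 |
| Power, about | 81% | 82% | 83% | 85% | 89% | 92% |

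**5. Power and type I error under the plan's rule.** Simulation of 5,000 trials per scenario, 15 candidates, three of them prognostic with joint R² as shown:

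| R² | No added covariates | Plan's rule | Three always adjusted | Type I error, plan's rule |
|---|---|---|---|---|
| 0.05 | 81% | 80% | 83% | 4.7% |
| 0.10 | 81% | 81% | 84% | 4.9% |
| 0.20 | 81% | 82% | 88% | 4.3% |
| 0.30 | 80% | 81% | 92% | 3.7% |

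The Monte Carlo standard error is √(0.8 × 0.2/5000) ≈ 0.6 points for power and √(0.05 × 0.95/5000) ≈ 0.3 points for type I error. The rule therefore performs about the same as adding nothing.

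**6. A second set-up.** With a single covariate whose correlation with the outcome beyond the fixed terms is 0.3, 0.5 or 0.7 (20,000 trials each), power under the rule is 81.6%, 82.0% and 83.0%, against 84.6%, 90.7% and 97.9% if it is always included. Type I error under the rule is 4.9%, 4.4% and 3.4%. The conclusion is the same.

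**The case against.** **The core of the model is fixed.** Baseline drinking is plausibly the strongest single predictor of follow-up drinking, and it is always in. This stands. A reader might infer that chance decides the primary model; the Aim 1 section does not support that. Chance decides only the extra terms.

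**Candidates are screened for relevance.** The plan compares arms by "comparing the initial groups on key variables that could be associated with the outcomes". This also stands: the pool is meant to exclude irrelevant variables, and a simulation in which 12 of 15 candidates are noise is not taken from the text. It does not rescue the rule. Within a pool of relevant variables, the significance test still discards each one about 95% of the time.

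**The gain may be small.** The documents give no R², and some obvious additions overlap with what is there: the AUDIT total contains consumption items, so it shares information with baseline TLFB. At R² of 0.02 to 0.05 the gain is only 1 to 2 points. If d = 0.30 refers instead to the raw SD and baseline correlates 0.5 with the outcome (assumed), the fixed model already has 0.30/√0.75 × √90 = 3.286, about 91% power, and a further R² of 0.10 brings it to about 93%. This stands as a limit on size.

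**No validity harm.** A reader might infer a raised false-positive rate or an underpowered trial. Neither is supported: type I error does not exceed 5%, and power under the rule meets the stated 80%.

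**Comparing arms can reveal faulty allocation.** True, and a descriptive baseline table remains worthwhile. That is a reason to look at balance, not a reason to let the test choose covariates.

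**Conclusion.** The point holds in a limited form. Beyond the baseline outcome value, time, treatment and the peer/clinician random effect, further baseline covariates enter the Aim 1 and Aim 2 models through significance tests on an unlisted set. Such a rule omits a prognostic variable about 95% of the time and in effect never admits sex or AUD.

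The harm is lost efficiency and incomplete prespecification, not bias or a raised error rate. For a linear outcome with 360 analysed and d = 0.30, power is 80–82% under the rule, against about 82% to 92% with a prespecified list as the incremental R² runs from 0.02 to 0.30. The omission rate rests only on correct randomisation and a 5% test level. The result for the stratification factors rests also on the block design and the assumed AUD share. The power gain depends on an R² that the documents do not supply, so it should be read as a range. The plan deserves correcting because the better method costs almost nothing, not because the result would otherwise be unsound.

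**What to change.** In the General analytic approach, delete the significance trigger for baseline covariates. In the Aim 1 and Aim 2 sections, name a fixed list that enters every efficacy model whatever the observed balance:

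- the baseline value of the outcome (already planned; for Aim 2 this is the baseline TSR value);
- sex;
- the AUD stratum, or the continuous AUDIT total from screening in its place;
- optionally, a few named measures already in Table 2 and judged prognostic, such as PHQ-9 and the readiness ruler;
- for Aim 2, optionally, visits in the year before entry from the planned record review. This partly overlaps the baseline TSR value, so it is an addition and not a necessity.

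Describe baseline balance in a table without using tests to choose covariates. Adjustment for chance imbalances can stay as a labelled sensitivity analysis. The rule on predictors of attrition serves the missing-data assumption and need not change, but the plan should label it as serving that purpose.

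The cost is a few sentences. All the variables are already collected or extracted, and the number randomised stays at 450. The list should be fixed before anyone examines baseline data by arm.
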